### 5.1 Visit and Analysis Time Period Classification

The time windows in this section reflect the administrative range around each visit for analysis. They are wider than those stated in the protocol to reduce missing values by capturing as many observation dates as possible. [Table 1](#) provides the convention to classify assessment dates into protocol-defined visits and analysis time periods for assessments at every visit, such as Hb and vital signs. [Table 1](#) will also be used for liver function assessments.

[Table 2](#) presents visit windows for values according to a slightly less frequent assessment schedule, i.e., the iron indices. And, [Table 2](#) will also be used for all other assessments, such as periodic complete blood count (CBC) with differential, chemistry laboratory tests, C-reactive protein (CRP), urine albumin-to-creatinine ratio (uACR) and lipids etc.

Unless otherwise specified, all assessments will be mapped to visit windows on the basis of the date of the assessment relative to the first dose date (i.e., Study Day), regardless of subject disposition or the CRF page completed, e.g., "Unscheduled", "End of Treatment", "End of Study", scheduled visit number. Similarly, all values collected within a reporting period will be considered for identification of safety events of interest.

If more than 1 laboratory-based efficacy outcome value (e.g., Hb, ferritin, hepcidin, TSAT, serum iron, TIBC, and lipids) is available in an analysis time period post-baseline, the average of all observed values (at most 1 per day) will be assigned to that period. For example, the window for the primary efficacy outcome, analysis time period 3, includes any Hb value (at most 1 per day) assessed between Study Days 155 to 266, corresponding to Weeks 24, 28, 32, and 36 (Visits 10 through 13).

Efficacy evaluations will use Hb values as assessed by the central laboratory. (Local HemoCue Hb values are used only for dose adjustments.)

When more than 1 assessment is made for other measures (not part of laboratory-based efficacy) within a given visit window post-baseline, the value of the assessment closest to the end of the window is the value associated with that visit for summaries over time. Most summaries of results by visit (e.g., laboratory or vital sign results for general safety) will use the single value

Statistical Analysis Plan AKB-6548-CI-0014 and AKB-6548-CI-0015

for each visit determined by this convention. Notable exceptions to this convention are the primary efficacy outcome and clinically significant changes.

If no assessment is available within a time window, then the associated visit and week classifications will be missing.

**Table 1. Classification of Assessments at Every Visit for Years 1 through 4**

| Time Period   | Visit Classification           | Target Week | Target Day | Actual Study Day of Visit            |
|---|--------------------------------|-------------|------------|--------------------------------------|
| Baseline  | Screening Visit 1 a | -           | -          | -                                    |
|   | Screening Visit 2 a | -           | -          | -                                    |
|   | Visit 1                        | Week 0      | Day 1      | Day 1 (first dose date) b |
| 1) Weeks 2-8  | Visit 2                        | Week 2      | Day 14     | Day 2-21                             |
|   | Visit 3                        | Week 4      | Day 28     | Day 22-35                            |
|   | Visit 4                        | Week 6      | Day 42     | Day 36-49                            |
|   | Visit 5                        | Week 8      | Day 56     | Day 50-63                            |
| 2) Weeks 10-20                                      | Visit 6                        | Week 10     | Day 70     | Day 64-77                            |
|   | Visit 7                        | Week 12     | Day 84     | Day 78-98                            |
|   | Visit 8                        | Week 16     | Day 112    | Day 99-126                           |
|   | Visit 9                        | Week 20     | Day 140    | Day 127-154                          |
| 3) Primary Efficacy Period (PEP)
(Weeks 24-36)   | Visit 10                       | Week 24     | Day 168    | Day 155-182                          |
|   | Visit 11                       | Week 28     | Day 196    | Day 183-210                          |
|   | Visit 12                       | Week 32     | Day 224    | Day 211-238                          |
|   | Visit 13                       | Week 36     | Day 252    | Day 239-266                          |
| 4) Secondary Efficacy Period (SEP)
(Weeks 40-52) | Visit 14                       | Week 40     | Day 280    | Day 267-294                          |
|   | Visit 15                       | Week 44     | Day 308    | Day 295-322                          |
|   | Visit 16                       | Week 48     | Day 336    | Day 323-350                          |
|   | Visit 17                       | Week 52     | Day 364    | Day 351-406                          |
| -   | Visit 18                       | Week 64     | Day 448    | Day 407-490                          |
| -   | Visit 19                       | Week 76     | Day 532    | Day 491-574                          |
| -   | Visit 20                       | Week 88     | Day 616    | Day 575-672                          |
| -   | Visit 21                       | Week 104    | Day 728    | Day 673-770                          |
| -   | Visit 22                       | Week 116    | Day 812    | Day 771-854                          |
| -   | Visit 23                       | Week 128    | Day 896    | Day 855-938                          |
| -   | Visit 24                       | Week 140    | Day 980    | Day 939-1036                         |
| -   | Visit 25                       | Week 156    | Day 1092   | Day 1037-1134                        |
| -   | Visit 26                       | Week 168    | Day 1176   | Day 1135-1218                        |
| -   | Visit 27                       | Week 180    | Day 1260   | Day 1219-1302                        |
| -   | Visit 28                       | Week 192    | Day 1344   | Day 1303-1400                        |
| -   | Visit 29                       | Week 208    | Day 1456   | Day 1401-1498                        |

a. The Screening period, which starts when the informed consent form is signed, will last a maximum of 8 weeks. Two Screening visits (Screening Visit 1 and Screening Visit 2) must be performed within 8 weeks prior to dosing (Baseline visit or Day 1). There must be a minimum of 4 days between the two Screening visits and a minimum of 4 days between Screening Visit 2 or last retest and the Baseline visit.

b. If patient has no first dose date, day 1 will be the randomization date.

**Table 2. Classification of assessments at select visits for Years 1 through 4**

| Time Period   | Visit Classification           | Target Week | Target Day | Actual Study Day of Visit            |
|---|--------------------------------|-------------|------------|--------------------------------------|
| Baseline  | Screening Visit 1 a | -           | -          | -                                    |
|   | Screening Visit 2 a | -           | -          | -                                    |
|   | Visit 1                        | Week 0      | Day 1      | Day 1 (first dose date) b |
| 1) Weeks 2-8  | Visit 3                        | Week 4      | Day 28     | Day 2-42                             |
|   | Visit 5                        | Week 8      | Day 56     | Day 43-63                            |
| 2) Weeks 10-20                                      | Visit 7                        | Week 12     | Day 84     | Day 64-112                           |
|   | Visit 9                        | Week 20     | Day 140    | Day 113-154                          |
| 3) Primary efficacy period (PEP)
(Weeks 24-36)   | Visit 11                       | Week 28     | Day 196    | Day 155-224                          |
|   | Visit 13                       | Week 36     | Day 252    | Day 225-266                          |
| 4) Secondary efficacy period (SEP)
(Weeks 40-52) | Visit 15                       | Week 44     | Day 308    | Day 267-336                          |
|   | Visit 17                       | Week 52     | Day 364    | Day 337-406                          |
| -   | Visit 18                       | Week 64     | Day 448    | Day 407-490                          |
| -   | Visit 19                       | Week 76     | Day 532    | Day 491-574                          |
| -   | Visit 20                       | Week 88     | Day 616    | Day 575-672                          |
| -   | Visit 21                       | Week 104    | Day 728    | Day 673-770                          |
| -   | Visit 22                       | Week 116    | Day 812    | Day 771-854                          |
| -   | Visit 23                       | Week 128    | Day 896    | Day 855-938                          |
| -   | Visit 24                       | Week 140    | Day 980    | Day 939-1036                         |
| -   | Visit 25                       | Week 156    | Day 1092   | Day 1037-1134                        |
| -   | Visit 26                       | Week 168    | Day 1176   | Day 1135-1218                        |
| -   | Visit 27                       | Week 180    | Day 1260   | Day 1219-1302                        |
| -   | Visit 28                       | Week 192    | Day 1344   | Day 1303-1400                        |
| -   | Visit 29                       | Week 208    | Day 1456   | Day 1401-1498                        |

a. The Screening period, which starts when the informed consent form is signed, will last a maximum of 8 weeks. Two Screening visits (Screening Visit 1 and Screening Visit 2) must be performed within 8 weeks prior to dosing (Baseline visit or Day 1). There must be a minimum of 4 days between the two Screening visits and a minimum of 4 days between Screening Visit 2 or last retest and the Baseline visit.

b. If patient has no first dose date, day 1 will be the randomization date.

## 5.2 Definition of Baseline

In general, the baseline value will also be the value of assessment closest to the end of the window, i.e., Day 1 (first dose date). The baseline value must be assessed prior to initiation of study treatment. In contrast, the baseline value for laboratory-based efficacy outcomes (e.g., Hb, ferritin, hepcidin, TSAT, serum iron, TIBC, and lipids) will be an average of the last 1 or 2 values prior to or on the first dose date, as specified in [Section 9.1.1](#).

## 5.3 Prior and Concomitant Medication

Prior and concomitant medications will be coded using World Health Organization Drug Dictionary (WHO DD; Mar 2017 or latest version) and summarized for each treatment group based on the safety population. Prior medication is defined as any medication taken prior to the

first dose of the study medication in the initial treatment period. Any medication taken on or after the day of first dose of the study treatment will be considered as concomitant medication for the treatment analysis.

#### 5.4 Handling of Missing Data

Missing data will be handled using a procedure specific to each variable and particular analysis as described in the sections relevant to each endpoint. If no method for missing data is discussed, descriptive analyses will be based upon observed data without imputation. [Appendix B](#) describes the general approaches to be used for missing data.

For the analysis of safety variables, only partial dates will be imputed unless otherwise specified. The algorithms for imputation of partial dates depend upon the parameter, as follows.

Adverse event onset:

- If onset date is completely missing, date is set to date of first dose.
- If year is present and month and day are missing or year and day are present and month is missing:
  - If year = year of first dose, then set month and day to month and day of first dose.
  - If year < year of first dose, then set month and day to December 31.
  - If year > year of first dose, then set month and day to January 1.
- If month and year are present and day is missing:
  - If year = year of first dose and
    - month = month of first dose, then set day to day of first dose date.
    - month < month of first dose, then set day to last day of month.
    - month > month of first dose, then set day to first day of month.
  - If year < year of first dose, then set day to last day of month.
  - If year > year of first dose, then set day to first day of month.
- For all other cases, set date to date of first dose.

Adverse event end date:

- If year is present and month and day are missing or year and day are present and month is missing, set end month and day to December 31.
- If month and year are present and day is missing, set the day to last day of the month.
- If fatal event, date is set to minimum of imputed end date and death date.
- For all other cases, set date to missing.

Concomitant medication:

- If start date is completely missing, start date will not be imputed.
- If start year is present and month and day are missing or year and day are present and month is missing, set start month and day to January 1.
- If start year and month are present and day is missing, set start day to 1st day of month.

Statistical Analysis Plan AKB-6548-CI-0014 and AKB-6548-CI-0015

- If end date is completely missing, end date will not be imputed.
- If end year is present and month and day are missing or year and day are present and month is missing, set end month and day to December 31.
- If end year and month are present and day is missing, set end day to last day of the month.
- The imputed dates must be logical, ensuring that no end date is after database lock or death or before the start date.

If site queries fail to resolve partial dates for laboratory values and vital signs, including for efficacy, the date is missing and will not be imputed.

## 6 EFFICACY ENDPOINTS

This section lists the efficacy endpoints; [Section 9](#) describes their definitions and the plans for the analysis of each endpoint.

### 6.1 Primary Efficacy Endpoint

The primary efficacy endpoint is change in average Hb between Baseline and the PEP (Weeks 24 to 36).

### 6.2 Key Secondary Efficacy Endpoints

Change in average Hb value between Baseline and the SEP (Weeks 40 to 52).

### 6.3 Other Efficacy Endpoints

This section describes the other efficacy endpoints of the studies.

#### 6.3.1 Definition of Rescue Episode

For summaries of potential rescue therapies (i.e., red blood cell [RBC] transfusion, and ESA), exposure to the therapy will be grouped temporally into episodes, which could contain multiple administrations based on the gap in time between the end of 1 and the start of the next. For ESA medication, the longest such gap within a single episode is 30 days, while the maximum gap is 7 days for RBC transfusion.

#### 6.3.2 Endpoints Related to Hb

The following efficacy endpoints are related to Hb:

- Change in average Hb value between Baseline and the combined PEP and SEP (Weeks 24 to 52)
- Having average Hb value in the geography-specific target range in Weeks 24 to 36 (yes/no variable)
- Having average Hb value in the geography-specific target range in Weeks 40 to 52 (yes/no variable)
- Having at least 1 Hb value in the geography-specific target range in Weeks 24 to 36 (yes/no variable)

Statistical Analysis Plan AKB-6548-CI-0014 and AKB-6548-CI-0015

- Having at least 1 Hb value in the geography-specific target range in Weeks 40 to 52 (yes/no variable)
- Having Hb values in the geography-specific target range for at least 1/2 of the observations in Weeks 24 to 36 (yes/no variable)
- Having Hb values in the geography-specific target range for at least 1/2 of the observations in Weeks 40 to 52 (yes/no variable)

These endpoints apply only to study CI-0014:

- Hb increase of >1.0 g/dL from Baseline to Week 52 (yes/no variable)
- Time to achieve Hb increase of >1.0 g/dL from Baseline Hb (censored at Week 52)

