5.3 Secondary Efficacy Endpoints

The key secondary efficacy endpoints include the following:

- Mean change in Hb value between Baseline (mean pretreatment Hb) and the secondary evaluation period (Weeks 40-52)
- Proportion of subjects with Hb values within the target range during the primary evaluation period (Weeks 24-36)
- Proportion of subjects with Hb values within the target range during the secondary evaluation period (Weeks 40-52)

Other secondary efficacy endpoints include:

- Proportion of time with Hb values within the target range during the primary evaluation period (Weeks 24-36)
- Proportion of time with Hb values within the target range during the secondary evaluation period (Weeks 40-52)
- Proportion of subjects with Hb increase of >1.0 g/dL from Baseline

- Time to achieve Hb increase of >1.0 g/dL from Baseline
- Mean change in Hb between Baseline (mean pretreatment Hb) and the primary evaluation period (mean Hb from Weeks 24-36) stratified by pre-baseline ESA exposure
- Progression of CKD
- Proportion of subjects receiving IV iron therapy from Baseline visit to Week 52
- Mean monthly dose of IV elemental iron administered from Baseline to Week 52 in subjects who have received IV iron
- Proportion of subjects receiving RBC transfusion(s) from Baseline to Week 52
- ESA rescue
- Dose adjustments from Baseline to Week 52
-

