**Table 3. Other Efficacy Endpoints**

| Endpoint  | Approach to Analysis   | Comments   |
|---|--|--|
| Hb endpoints – Section 6.3.2  |  |  |
| Change in average Hb value between Baseline and the combined primary efficacy period (PEP) and secondary efficacy periods (SEP) (Weeks 24-52) | Analysis of covariance (ANCOVA) stratified by baseline strata. | Average may include imputed values for PEP and/or SEP.   |
| Having Hb values in the geography-specific target range during PEP or SEP (2 alternate definitions)   | Mantel-Haenszel test stratified by the baseline strata         | This analysis includes the observed hemoglobin values.   |
| CI-0014 only: Hb increase of >1.0 g/dL from Baseline to any time before Week 52   | Mantel-Haenszel test stratified by baseline strata             | This analysis includes the observed hemoglobin values.   |
| CI-0014 only: Time to achieve Hb increase of >1.0 g/dL from Baseline Hb (censored at Week 52)   | Time – to – event  | This analysis will use only observed data.   |
| Progression of CKD ( Section 6.3.6 )  |  |  |
| Progression of CKD (entire length of study)   | Time – to – event  |  |
| Iron endpoints ( Section 6.3.3 )  |  |  |
| Receipt of at least 1 administration of elemental iron ( IV, or oral)   | Mantel-Haenszel test stratified by baseline strata             |  |
| Average weekly dose of elemental iron, IV, or oral  | ANCOVA stratified by baseline strata.                          | If the distribution is highly skewed either because of a large spike at zero or a long tail to the right (or both), other methods may be considered. |

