## APPENDIX D. ANALYSIS OF NON-NORMAL ENDPOINTS

### D.1. Analysis of Binary Endpoints

This section describes the methods for analyzing other binary endpoints.

For each binary endpoint, a 95% confidence interval will be calculated for each proportion by treatment group using the Clopper-Pearson method [Clopper, 1934].

For analyses conducted in the randomized population, the weighted difference in proportions between treatment groups, adjusting for the stratification factors, and the corresponding 2-sided 95% confidence interval will be calculated by weighting according to the Mantel-Haenszel method. The associated odds ratio and corresponding 2-sided 95% confidence interval will also be calculated. Subgroup analysis will be conducted similarly.

The below efficacy endpoints have binary outcome measures and will use the code structure presented in [Exhibit D 1](#). For the first 4 endpoint, noninferiority will have been established if the lower limit of the confidence interval for the risk difference is above -15%.

- At least 1 Hb value in the geography-specific target range in Weeks 24 to 36
- At least 1 Hb value in the geography-specific target range in Weeks 40 to 52
- Hb values in the geography-specific target range for at least 1/2 of the observations in Weeks 24 to 36
- Hb values in the geography-specific target range for at least 1/2 of the observations in Weeks 40 to 52
- Hb increase of >1.0 g/dL in Year 1 (CI-0014)
- Receipt of at least 1 administration of elemental iron, repeated using each route, intravenous (IV), or oral
- Receipt of any red blood cell (RBC) transfusion
- Receipt of any erythropoietin-stimulating agent (ESA) rescue medication
- Receipt of any rescue therapy (series of definitions from narrow to broad)
- Hb values >12, 13, or 14 g/dL
- Hb values <8 or 9 g/dL
- Hb increase of >1.0 g/dL within any 2-week period (CI-0015)
- Hb increase of >2.0 g/dL within any four-week period (CI-0015)

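### The protocol's time-in-range endpoints have no analysis in the SAP, and the nearest SAP endpoint, a half-of-readings rule, sets a hurdle that depends on how many readings a subject has

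*SAP*

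**What the plan says.** Protocol (Amendment 7-COL), Section 5.3, lists among the other secondary endpoints "Proportion of time with Hb values within the target range during the primary evaluation period (Weeks 24-36"), with a matching entry for Weeks 40-52. The synopsis repeats both. No method of computation is given.

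SAP Section 1 states that the SAP's methods prevail over the protocol's where they differ. Neither Section 6.3.2 nor Table 3 has a time-in-range endpoint. Section 6.3.2 has yes/no variables instead: period-average Hb in range, at least one value in range, and "Having Hb values in the geography-specific target range for at least 1/2 of the observations in Weeks 24 to 36 (yes/no variable"), each repeated for Weeks 40-52. Table 3 labels the last two kinds "Having Hb values in the geography-specific target range during PEP or SEP (2 alternate definitions") and comments: "This analysis includes the observed hemoglobin values".

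Appendix D.1 lists "Hb values in the geography-specific target range for at least 1/2 of the observations in Weeks 24 to 36" as the third of its binary endpoints. For the first four it says that "noninferiority will have been established if the lower limit of the confidence interval for the risk difference is above -15" percent. On the interval it says that "the corresponding 2-sided 95% confidence interval will be calculated by weighting according to the Mantel-Haenszel method".

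The number of readings is not fixed. Section 5.1 says that the window for Weeks 24-36 "includes any Hb value (at most 1 per day) assessed between Study Days 155 to 266, corresponding to Weeks 24, 28, 32, and 36". Section 2.2 says that no laboratory assessments are planned after permanent discontinuation of study drug. The SAP sets no minimum number of readings for this rule and does not say whether an observation is a visit or a value.

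**The concern.** There are two linked problems. First, two listed secondary endpoints have dropped out of the prevailing analysis document without comment. Second, the item closest to them is built on a threshold that moves with the denominator. Because exactly half counts as success, one fewer reading can raise the required share from 50% to 67%, and one fewer again lowers it back to 50%. The endpoint therefore reflects attendance as well as Hb control. In an open-label trial attendance can differ between arms, and Appendix D.1 attaches a formal noninferiority statement to the result.

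**Working it through.** **Inputs from the documents.** Success means at least half of n readings in range (SAP 6.3.2, D.1). Four visits are scheduled in Weeks 24-36 (SAP Table 1). Target ranges are 10-11 g/dL in the US and 10-12 g/dL elsewhere (SAP 2.3). The margin is -15% on the Mantel-Haenszel risk difference (D.1).

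**Inputs assumed, because the documents do not give them.** p is the chance that one reading is in range. Between-patient SD is 0.4-0.8 g/dL and within-patient SD 0.6-0.8 g/dL. The mean is at mid-range (10.5 US, 11.0 elsewhere), and Hb is reported to 0.1 g/dL.

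The SAP states no success rate or power for this rule, so there is no figure of its own to reproduce. The power of roughly 90% in Sections 9.3.1 and 9.3.2 belongs to the period-average endpoints.

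**Step 1: the hurdle.** The number needed is n/2 rounded up.

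| n | needed | share |
|---|---|---|
| 1 | 1 | 100% |
| 2 | 1 | 50% |
| 3 | 2 | 67% |
| 4 | 2 | 50% |
| 5 | 3 | 60% |

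**Step 2: independent readings.** Success is the upper binomial tail from the number needed. At p = 0.5 and n = 1 to 5 it is 50.0%, 75.0%, 50.0%, 68.75%, 50.0%. A fourth reading turns failure into success when exactly one of three was in range and the fourth is too, so the 4-versus-3 gap is 3p²(1-p)²:
- p = 0.5: 3 × 0.25 × 0.25 = 18.75 points, the maximum
- p = 0.7: 3 × 0.49 × 0.09 = 13.2 points
- p = 0.8: 3 × 0.64 × 0.04 = 7.7 points

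**Step 3: correlated readings.** Each subject is given a true mean and readings scattered around it, with 400,000 simulated subjects per setting. For the US range with both SDs 0.6, success at n = 1 to 5 is 48%, 71%, 49%, 64%, 49%. Over the assumed SDs the 4-versus-3 gap is about 14-18 points in the US range and about 5-12 points in the non-US range. Putting a correlation directly on the in-range indicator at p = 0.5 gives smaller gaps: 12.9 points at a correlation of 0.2, 10.7 at 0.3, 7.0 at 0.5 and 5.5 at 0.6.

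**Step 4: effect on the arm comparison.** The shift in the risk difference is (arm difference in the share of subjects with 3 rather than 4 readings) × (4-versus-3 gap). For a 20-point imbalance:
- US: 0.20 × 14 = 2.8 to 0.20 × 18 = 3.6 points
- non-US: 0.20 × 5 = 1.0 to 0.20 × 12 = 2.4 points

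Using up 15 points this way would need an imbalance of 0.15/0.1875 = 80 points under independence. At an in-range correlation of 0.3 it would need 0.15/0.1066 = 141 points, which is impossible. If visits are missed at random, 5% in one arm and 20% in the other, with p = 0.5, success is 65.6% versus 61.5% (4.1 points) under independence and 58.9% versus 57.1% (1.8 points) at a correlation of 0.3.

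**Step 5: does a proportion cure it?** The expected share of readings in range is p for every n, so the odd/even effect disappears. Changing the rule to strictly more than half does not help. At p = 0.5 and n = 1 to 4 it gives 50%, 25%, 50%, 31.25%, which is the same effect reversed.

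**The case against.** The strongest reply is that the margin judges the difference between arms, while the 14-18 points separate subjects with different counts. Both arms follow one schedule of visits and assessments (SAP 2.5; protocol 8.4.3), so most of the parity effect cancels. No figure in the documents supports a 20-point imbalance. This stands. A reader might infer from the size of the gap that reading counts could consume the whole -15% margin, but Step 4 shows that they could not under any plausible imbalance.

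A reader might also infer that the SAP substituted the half-of-readings rule for time in range. The documents do not say so. Table 3 presents it as one of two alternate definitions of having Hb values in range. What the documents do show is that the time-in-range endpoints are absent and that this rule is the nearest item.

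The endpoint is also exploratory, with no multiplicity correction (SAP 9.3). Only the primary endpoint and the Week 40-52 change in Hb are formally ordered (SAP 9.2), and the period-average in-range endpoints do not use this rule. All of that stands and limits the consequence.

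Counts above 4 depend on reading Section 5.1 literally. Appendix B.3 speaks of up to four per-visit observations for the period average. The 3-versus-4 contrast does not depend on which reading is right, but the difference shows that the denominator needs defining.

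**Conclusion.** The point holds in a limited form. Two secondary endpoints of the current protocol have no analysis in the SAP, and the closest SAP endpoint has a hurdle that varies with the parity of the reading count. The dependence on parity is arithmetic and needs no assumption. Its size does: about 14-18 points (US) and 5-12 points (non-US) between 4 and 3 readings rests on the assumed SDs and mid-range means, and stronger within-subject correlation would shrink it. The effect on the arm comparison is about 1-4 points for a 20-point imbalance in counts. That is a modest distortion of an exploratory result. It does not threaten the -15% margin, and it has no bearing on the primary or key secondary analysis. The change is worth making because it is cheap and restores what the protocol lists.

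**What to change.** Add to SAP 6.3.2 and Table 3, for Weeks 24-36 and Weeks 40-52, each subject's proportion of observed central-laboratory Hb readings (or of time) in the geography-specific range. Compare the arms with the ANCOVA stratified by baseline strata that Table 3 already uses. State what counts as a reading and how subjects with none are handled.

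Keep the half-of-readings rows as descriptive only, remove them from the -15% noninferiority statement in Appendix D.1, and tabulate the number of readings per subject by arm and period.

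Linear interpolation to estimate time in range, or deleting the half-of-readings rows, are options and not required corrections.

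The cost is SAP wording and a short derivation from data already collected. A proportion based on few readings is imprecise for an individual subject. If time is interpolated instead, the method assumes a straight line between visits about four weeks apart.
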